# 7. RATIONALE AND BACKGROUND

Tofacitinib citrate (Xeljanz®) is an oral Janus kinase inhibitor approved by the European Commission (EC) in March 2017 as an immediate-release film-coated tablet (5 mg), taken twice daily (BID), for the treatment of adults with moderate-to-severe active rheumatoid arthritis (RA) who have had inadequate response or intolerance to one or more disease-modifying antirheumatic drugs (DMARDs). The EC subsequently approved a prolonged-release film-coated tablet (11 mg), taken once daily (QD), in December 2019. RA is a chronic systemic autoimmune disease characterized by inflammation and progressive destruction of joints. Despite a number of treatment options available, many patients do not sustain remission. In clinical trials, patients treated with 5 mg of tofacitinib BID, in combination with methotrexate (MTX), showed significantly reduced disease activity scores and improved physical functioning and general health status as compared to patients on placebo. The approved dose of tofacitinib for the treatment of moderate-to-severe active RA is 5 mg BID or prolonged-release 11 mg QD, which should not be exceeded, in combination with MTX; it may also be given as monotherapy in the case of intolerance to MTX or when treatment with MTX is inappropriate.

In June 2018, tofacitinib 5-mg tablet (immediate-release) was approved by the EC, in combination with MTX, for the treatment of active psoriatic arthritis (PsA) in adults with inadequate response or intolerance to a prior DMARD therapy. PsA is an inflammatory arthritis occurring in between 6%-42% of patients with psoriasis. In clinical trials, patients treated with 5 mg of tofacitinib BID, in combination with a non-biologic DMARD, achieved significantly improved clinical response and physical functioning over the 6- and 12-month study periods. The approved dose of tofacitinib for the treatment of active PsA is 5 mg BID, which should not be exceeded.

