Finally, in July 2018, tofacitinib 5-mg tablet and 10-mg tablet (immediate release) were approved by the EC for the treatment of moderately-to-severely active ulcerative colitis (UC) in patients with an inadequate response, a loss of response, or an intolerance to conventional therapy or a biologic agent. UC is a bowel disease characterized by inflammation and ulcers in the colon and rectum. In clinical trials, patients treated with 5 mg or 10 mg of tofacitinib BID were more likely to achieve and/or maintain a clinical response and remission of their condition as compared to patients in the placebo group. At the time of initial approval, the doses of tofacitinib for the treatment of moderately-to-severely active UC were 10 mg BID for induction (up to a 16-week period) and 5 mg BID for maintenance, which should not be exceeded.

The following table summarizes the date tofacitinib was approved by the EC and the approved dose for each of the 3 approved indications as of June 2021.

Indication	Date approved by the EC	Approved dose
RA	March 2017	5 mg immediate-release tablets BID
	December 2019	11 mg prolonged release tablets QD
PsA	June 2018	5 mg immediate-release tablets BID
UC	July 2018	5 mg or 10 mg immediate-release tablets BID

Table 1.	Summary of appro	oved indications and	dosages for tofacitinib
----------	------------------	----------------------	-------------------------

Abbreviations: EC = European Commission; PsA = psoriatic arthritis; RA = rheumatoid arthritis; UC = ulcerative colitis.

**Note:** BID is an abbreviation for "bis in die," which in Latin means twice a day; QD is an abbreviation for "quaque die," which in Latin means once a day.

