Serious and opportunistic infections of interest (including HIV, HZ, TB, and viral hepatitis B and	Comorbidity	Defined as $\geq 1$ ICD-10 diagnosis code for a serious and/or opportunistic infection of interest.
C)		DIAGNOSIS CODES FOR SELECT INFECTIONS OF INTEREST.
Diverticulitis	Comorbidity	Defined as ≥1 ICD-10 diagnosis code for diverticulitis.

 Table 3.
 Operational definitions of study variables in the selected databases

° The data sources are unable to reliably ascertain severity of hepatic impairment and renal impairment.

<sup>p The data sources may not be able to differentiate between active and latent TB.

Variable	Role	Operational definition
Malignancy (non- metastatic and metastatic, excluding non-melanoma skin cancer)	Comorbidity	Defined as ≥1 ICD-10 diagnosis code for a malignancy (excluding non-melanoma skin cancer).
Non-melanoma skin cancer	Comorbidity	Defined as ≥1 ICD-10 diagnosis code for non-melanoma skin cancer.
Gastrointestinal perforation	Comorbidity	Defined as $\geq 1$ ICD-10 diagnosis code for gastrointestinal perforation.
Interstitial lung disease	Comorbidity	Defined as ≥1 ICD-10 diagnosis code for interstitial lung disease.
		Complete list in ANNEX 4. LIST OF DIAGNOSIS AND PROCEDURE CODES FOR INTERSTITIAL LUNG DISEASE.
Diabetes	Comorbidity	Defined as ≥1 ICD-10 diagnosis code for diabetes.
Immunodeficiencies of interest	Comorbidity	Defined as $\geq$ 1 ICD-10 diagnosis code for immunodeficiency.
		Complete list in ANNEX 5. LIST OF DIAGNOSIS CODES FOR SELECT IMMUNODEFICIENCIES OF INTEREST.
Prior use of corticosteroids	Medication history	Defined as ≥1 prescription dispensing of a corticosteroid (as identified by ATC code[s]) in the 12 months prior to the index tofacitinib dispensing.
		Complete list in ANNEX 7. LIST OF ATC CODES FOR COMEDICATIONS OF INTEREST.
Prior use of statins	Medication history	Defined as $\geq 1$ prescription dispensing of a statin (as identified by ATC code[s]) in the 12 months prior to the index tofacitinib dispensing.
		Complete list in ANNEX 7. LIST OF ATC CODES FOR COMEDICATIONS OF INTEREST.

 Table 3.
 Operational definitions of study variables in the selected databases

Variable	Role	Operational definition
Prior use of any biologic q	Medication history	Defined as ≥1 prescription dispensing of a biologic (as identified by ATC code[s]) in the 12 months prior to the index tofacitinib dispensing.

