		Complete list in ANNEX 6. LIST OF ATC CODES FOR MEDICATIONS OF INTEREST TO AVOID WHILE TAKING TOFACITINIB.
Prior use of conventional synthetic DMARDs (csDMARDs)	Medication history	Defined as ≥1 prescription dispensing of a csDMARD (as identified by ATC code[s]) in the 12 months prior to the index tofacitinib dispensing.
		Complete list in ANNEX 6. LIST OF ATC CODES FOR MEDICATIONS OF INTEREST TO AVOID WHILE TAKING TOFACITINIB.
Prior use of methotrexate (MTX)	Medication history	Defined as $\geq 1$ prescription dispensing of MTX (as identified by ATC code L04AX03) in the 12 months prior to the index tofacitinib dispensing.
Prior use of anti-TB therapy	Medication history	Defined as $\geq 1$ prescription dispensing of anti-TB therapy (as identified by ATC code[s]) in the 12 months prior to the index tofacitinib dispensing.
Prior vaccination r	Medication history	Defined as $\geq 1$ procedure code and/or $\geq 1$ prescription dispensing (as identified by ATC code[s]) for a vaccination, overall and stratified by live and non-live vaccinations in the 12 months prior to the index tofacitinib dispensing.
		Complete list in ANNEX 7. LIST OF ATC CODES FOR COMEDICATIONS OF INTEREST.

Table 3.	Operational	definitions of	f study	variables in	the selected	databases

<sup>q Biologics that are dispensed or administered primarily through hospital channels may not captured (completely) in the data sources.

<sup>r This variable will not be assessed in Sweden because most vaccinations are not done in specialist care and therefore are not captured in the NPR, nor are vaccines prescribed and purchased by the patients in the pharmacies and therefore are not be captured in the PDR. Vaccination data are also unavailable in the PHARMO Database Network. In GKV claims, it is not possible to differentiate between live and non-live vaccines.

Variable	Role	Operational definition
Concomitant use of a contraindicated immunomodulator csDMARD	Comedication	Defined as ≥1 overlapping days' supply of a tofacitinib prescription dispensing and a prescription dispensing for a contraindicated immunomodulator csDMARD (as identified by ATC code[s]) during the follow-up period.

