		Note: Concomitancy with a contraindicated csDMARD can occur even if the contraindicated medication is dispensed prior to the index tofacitinib dispensing, provided that there is $\geq 1$ overlapping days' supply with a tofacitinib prescription dispensing during the follow-up period.
		Duration of tofacitinib therapy defined in Section 9.3.3.
Concomitant use of MTX	Comedication	Defined as ≥1 overlapping days' supply of a tofacitinib prescription dispensing and a prescription dispensing for MTX (as identified by ATC code L04AX03) during the follow-up period.
		Note: Concomitancy with MTX can occur even if the medication is dispensed prior to the index tofacitinib dispensing, provided that there is $\geq 1$ overlapping days' supply with a tofacitinib prescription dispensing during the follow-up period.
		Duration of tofacitinib therapy defined in Section 9.3.3.
Concomitant use of a corticosteroid	Comedication	Defined as ≥1 overlapping days' supply of a tofacitinib prescription dispensing and a prescription dispensing for a corticosteroid (as identified by ATC code[s]) during the follow-up period.
		Note: Concomitancy with a corticosteroid can occur even if the medication is dispensed prior to the index tofacitinib dispensing, provided that there is $\geq 1$ overlapping days' supply with a tofacitinib prescription dispensing during the follow-up period.
		Duration of tofacitinib therapy defined in Section 9.3.3.

 Table 3.
 Operational definitions of study variables in the selected databases

Variable	Role	Operational definition	
Concomitant use of anti- TB therapy	Comedication	Defined as ≥1 overlapping days' supply of a tofacitinib prescription dispensing and a prescription dispensing for anti-TB therapy (as identified by ATC code[s]) during the follow-up period.	
		Note: Concomitancy with anti-TB therapy can occur even if the medication is dispensed prior to the index tofacitinib dispensing, provided that there is $\geq 1$ overlapping days' supply with a tofacitinib prescription dispensing during the follow-up period.	
		Duration of tofacitinib therapy defined in Section 9.3.3.	
Primary Objective 2: Prescribers' adherence to the tofacitinib aRMMs s			
Compliance to the recomm	ended posology per indication and o	luration of use t	
Duration of tofacitinib therapy	Utilisation	Defined in Section 9.3.3. Assessed during the follow-up period.	

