### ANNEX 7. LIST OF ATC CODES FOR COMEDICATIONS OF INTEREST

Class of drug	Drug	ATC code
Corticosteroids	Aldosterone	H02AA01
	Fludrocortisone	H02AA02
	Desoxycortone	H02AA03
	Betamethasone	H02AB01
	Dexamethasone	H02AB02
	Fluocortolone	H02AB03
	Methylprednisolone	H02AB04
	Paramethasone	H02AB05
	Prednisolone	H02AB06
	Prednisone	H02AB07
	Triamcinolone	H02AB08
	Hydrocortisone	H02AB09
	Cortisone	H02AB10
	Prednylidene	H02AB11
	Rimexolone	H02AB12
	Deflazacort	H02AB13
	Cloprednol	H02AB14
	Meprednisone	H02AB15
	Cortivazol	H02AB17
	Methylprednisolone, combinations	H02BX01
	Trilostane	H02CA01
	Phenylbutazone and corticosteroids	M01BA01
	Dipyrocetyl and corticosteroids	M01BA02
	Acetylsalicylic acid and corticosteroids	M01BA03
Methotrexate	Methotrexate	L04AX03
Statins	Somatostatin	H01CB01
	Atorvastatin	C10AA05
	Atorvastatin and acetylsalicylic acid	C10BX08
	Atorvastatin and amlodipine	C10BX03
	Atorvastatin and ezetimibe	C10BA05
	Atorvastatin and perindopril	C10BX15

Class of drug	Drug	ATC code
	Atorvastatin, acetylsalicylic acid and perindopril	C10BX12
	Atorvastatin, acetylsalicylic acid and ramipril	C10BX06
	Atorvastatin, amlodipine and perindopril	C10BX11
	Cerivastatin	C10AA06
	Fluvastatin	C10AA04
	Gemigliptin and rosuvastatin	A10BH52
	Imipenem and cilastatin	J01DH51
	Lovastatin	C10AA02
	Lovastatin and nicotinic acid	C10BA01
	Nystatin	A07AA02, D01AA01, G01AA01
	Nystatin, combinations	G01AA51
	Pentostatin	L01XX08
	Pitavastatin	C10AA08
	Pravastatin	C10AA03
	Pravastatin and acetylsalicylic acid	C10BX02
	Pravastatin and fenofibrate	C10BA03
	Rosuvastatin	C10AA07
	Rosuvastatin and acetylsalicylic acid	C10BX05
	Rosuvastatin and amlodipine	C10BX09
	Rosuvastatin and ezetimibe	C10BA06
	Rosuvastatin and valsartan	C10BX10
	Rosuvastatin, amlodipine and lisinopril	C10BX07
	Rosuvastatin, amlodipine and perindopril	C10BX14
	Rosuvastatin, perindopril and indapamide	C10BX13
	Simvastatin	C10AA01
	Simvastatin and acetylsalicylic acid	C10BX01
	Simvastatin and ezetimibe	C10BA02
	Simvastatin and fenofibrate	C10BA04
	Simvastatin, acetylsalicylic acid and ramipril	C10BX04
	Sitagliptin and simvastatin	A10BH51
	Somatostatin	H01CB01
Vaccinations	Anthrax antigen	J07AC01
	Brucella antigen	J07AD01

Class of drug	Drug	ATC code
	Cholera, inactivated, whole cell	J07AE01
	Cholera, live attenuated	J07AE02
	Cholera, combinations with typhoid vaccine, inactivated, whole cell	J07AE51
	Diphtheria toxoid	J07AF01
	Hemophilus influenzae B, purified antigen conjugated	J07AG01

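### As written, the code rules would count methotrexate under L01BA01 and intestinal or rectal corticosteroids (A07EA) as no use in the descriptive medication tables

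*Protocol*

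**What the plan says.** Protocol Section 9.3.2, Table 3, defines prior corticosteroid use as at least one "prescription dispensing of a corticosteroid (as identified by ATC code[s]) in the 12 months prior to the index tofacitinib dispensing" and describes Annex 7 as the complete list. The concomitant-corticosteroid row also relies on ATC codes but cites no annex.

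The Annex 7 corticosteroid class runs from aldosterone (H02AA01) to "Acetylsalicylic acid and corticosteroids" (M01BA03).

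For methotrexate the code stands in the definition itself. The prior-use row reads "MTX (as identified by ATC code L04AX03) in the 12 months prior to the index tofacitinib dispensing", and the concomitant-use row reads "prescription dispensing for MTX (as identified by ATC code L04AX03) during the follow-up period". Annex 7 repeats the same single code.

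The text introducing Table 3 says that its codes, and those in Annexes 3 to 7, are preliminary, are subject to sponsor review and/or approval before the study starts, and will be refined while the SAP is developed.

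On indications, Section 7 describes the UC approval as being for "patients with an inadequate response, a loss of response, or an intolerance to conventional therapy or a biologic agent" and the psoriatic arthritis approval as "in combination with MTX, for the treatment of active psoriatic arthritis (PsA) in adults". Prior and current medication, by country and indication, belongs to Primary Objective 1 (Section 8).

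**The concern.** A dispensing counts only if its code is on the list, so an unlisted code is indistinguishable from no treatment. Two gaps follow once the lists are set against the ATC classification, which the protocol adopts as its coding system.

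- **Corticosteroids.** ATC places intestinal and rectal steroid products in A07EA. None is listed, although the variable is any corticosteroid and UC is one of the three approved indications.
- **Methotrexate.** ATC also holds methotrexate as L01BA01. It is absent from the csDMARD list in Annex 6, so no other study variable would recover a user missed by L04AX03.

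There is also an error in the other direction. The class counts mineralocorticoids (H02AA) and trilostane (H02CA01, an agent that blocks steroid synthesis) as corticosteroid use.

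At stake are the reported proportions of patients with prior and concomitant corticosteroid and methotrexate use. More patients would not cure this, because it is misclassification and not sampling error.

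**Working it through.** **1. Count of the Annex 7 corticosteroid class**

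| ATC group | Codes | Number |
|---|---|---|
| H02AA | 01 to 03 | 3 |
| H02AB | 01 to 15, and 17 | 16 |
| H02BX | 01 | 1 |
| H02CA | 01 | 1 |
| M01BA | 01 to 03 | 3 |
| **Total** | | **24** |

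That is 21 codes in H02, 3 in M01BA and none in A07. Four of the 24 (three H02AA and one H02CA) are the doubtful inclusions.

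**2. Methotrexate.** One code, L04AX03, appears in Annex 7 and in both Table 3 rows. There is none in L01.

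**3. Is the narrow scope explained elsewhere?** Table 3 does not contain the word systemic. Annex 6 uses gut-group codes for other drugs (A07EC01, A07EC03, A07EC04) and L01 codes for rituximab (L01XC02) and mercaptopurine (L01BB02). So neither ATC group is outside the study's coding scope. These are not precedents for giving one drug two codes, since the two L01 drugs each have one. The limitations in Section 9.9 do not mention the gap.

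**4. Illustration of size.** The documents give no figures for steroid or methotrexate use and no shares by code. Both inputs are therefore assumptions: *p* is true use, and *s* is the share of users whose only dispensings carry unlisted codes.

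Reported use = *p*(1 − *s*); shortfall = *p* × *s*.

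The only yardstick in the protocol is its precision target. Section 9.5 gives 0.50 × 0.50 × 1.96² / 0.10² = 96.04, so 97 patients, rounded up to 100, for a half-width of 10 points. This reproduces. The half-width below is 1.96 × √[*o*(1 − *o*)/100], with *o* the reported proportion.

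| *p* | *s* | Reported | Shortfall (points) | Half-width at n = 100 (points) |
|---|---|---|---|---|
| 50% | 5% | 47.5% | 2.5 | 9.8 |
| 50% | 10% | 45% | 5 | 9.8 |
| 50% | 20% | 40% | 10 | 9.6 |
| 50% | 30% | 35% | 15 | 9.3 |

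Over the same range of *s*, the shortfall is 1.5 to 9 points at *p* = 30% and 3.5 to 21 points at *p* = 70%. At *p* = 50% it passes the half-width somewhere between *s* = 10% and *s* = 20%. Below that it is smaller than the sampling uncertainty at the minimum sample size. In the larger country-indication cells, where the interval is narrower, a smaller share would be enough.

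**The case against.** The strongest reply is that the lists are not final. Section 9.3.2 calls them preliminary and assigns refinement to the SAP, which is not at hand. That stands, and it means the plan cannot be said to have committed to counting these patients as non-users. It does not remove the point. The protocol states a specific rule, writes one methotrexate code into two definitions and labels the steroid annex complete. That is a narrow rule to correct, not a topic left open.

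Second, a list limited to systemic steroids may have been intended. That would be coherent, but the variable would then need that label. The same annex lists somatostatin, nystatin, pentostatin and imipenem with cilastatin as statins, which makes a deliberately curated scope less likely.

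Third, the contents of A07EA, H02CA and L01BA01 come from the ATC classification and not from the protocol. Nothing in the protocol shows how often any of the four databases records those codes. This is correct, and it is why no size can be asserted.

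Fourth, the concomitant-corticosteroid row does not cite Annex 7. So the steroid list is firmly tied only to prior use. It carries over to concomitant use only because it is the one corticosteroid list that the protocol offers.

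A reader might go further and infer that a comparison of RA/PsA with UC is biased, or that missed methotrexate would be reported as monotherapy. The documents support neither. Section 9.7.1 rules out comparative analyses, and no outcome in Section 9.3.1 classifies patients as on monotherapy or combination therapy. Nor does any outcome test prior conventional therapy in UC: the alternative therapy used throughout is a biologic.

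**Conclusion.** The point holds as a defect of definition with limited reach. As written, methotrexate dispensed only under L01BA01 would be counted as no use in both methotrexate rows. Intestinal or rectal steroids would be counted as no use in the prior-corticosteroid row, and in the concomitant row if the same list is applied. The steroid gap would fall mainly on UC. The four H02AA and H02CA codes work in the opposite direction, and because they concern different patients they would not correct the gap.

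At most four descriptive medication variables under Primary Objective 1 are affected. No adherence outcome under Primary Objective 2 and no planned comparison depends on them. The shortfall is unknown: 2.5 to 15 points at a true use of 50% rests wholly on the assumed 5% to 30% share of users with unlisted codes only. A database that holds all its methotrexate under L04AX03 would show no methotrexate shortfall. The conclusion also rests on the ATC classification for the content of the codes.

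**What to change.** Before the code lists are finalised:

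1. Ask each data holder which codes carry methotrexate, then identify it by L04AX03 or L01BA01 in both Table 3 rows and in Annex 7.
2. Report corticosteroids as systemic (the current list, cleaned) with a separate intestinal/rectal sub-row (A07EA). If only systemic use is wanted, label the variable systemic corticosteroids.
3. Remove trilostane (H02CA01) from the class. Report the mineralocorticoids (H02AA) separately or remove them.
4. Cite the same list in the concomitant-corticosteroid row.

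The cost is an edit to the code lists and two Table 3 definitions, plus one query to each data holder, before extraction begins (planned for 30 September 2022). The downside is that a few oncology methotrexate records may enter under L01BA01.

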### ANNEX 8. LIST OF ATC CODES FOR ANTIHYPERTENSIVES

Class of drug	Drug	ATC code
Antiadrenergic agents, centrally acting	rescinnamine	C02AA01
	reserpine	C02AA02
	combinations of rauwolfia alkaloids	C02AA03
	rauwolfia alkaloids, whole root	C02AA04
	deserpidine	C02AA05
	methoserpidine	C02AA06
	bietaserpine	C02AA07
	reserpine, combinations	C02AA52
	combinations of rauwolfia alkoloids, combinations	C02AA53
	bietaserpine, combinations	C02AA57
	rescinnamine	C02AA01
	methyldopa (levorotatory)	C02AB01
	methyldopa (racemic)	C02AB02
	clonidine	C02AC01
	guanfacine	C02AC02
	tolonidine	C02AC04
	moxonidine	C02AC05
	rilmenidine	C02AC06
Antiadrenergic agents,	trimetaphan	C02BA01
gangnon-blocking	mecamylamine	C02BB01
Antiadrenergic agents,	prazosin	C02CA01
peripherally acting	indoramin	C02CA02
	trimazosin	C02CA03
	doxazosin	C02CA04
	urapidil	C02CA06
	betanidine	C02CC01
	guanethidine	C02CC02
	guanoxan	C02CC03
	debrisoquine	C02CC04
	guanoclor	C02CC05

Class of drug	Drug	ATC code
	guanazodine	C02CC06
	guanoxabenz	C02CC07
Arteriolar smooth muscle,	diazoxide	C02DA01
agents acting on	dihydralazine	C02DB01
	hydralazine	C02DB02
	endralazine	C02DB03
	cadralazine	C02DB04
	minoxidil	C02DC01
	nitroprusside	C02DD01
	pinacidil	C02DG01
Other antihypertensives	veratrum	C02KA01
	metirosine	C02KB01
	pargyline	C02KC01
	ketanserin	C02KD01
	bosentan	C02KX01
	ambrisentan	C02KX02
	sitaxentan	C02KX03
	macitentan	C02KX04
	riociguat	C02KX05
	ambrisentan and tadalafil	C02KX52

### ANNEX 9. LIST OF ATC CODES FOR ANTIHYPERLIPIDAEMICS

Class of drug	Drug	ATC code
Lipid modifying agents, plain	simvastatin	C10AA01
	lovastatin	C10AA02
	pravastatin	C10AA03
	fluvastatin	C10AA04
	atorvastatin	C10AA05
	cerivastatin	C10AA06
	rosuvastatin	C10AA07
	pitavastatin	C10AA08
	clofibrate	C10AB01
	bezafibrate	C10AB02
	aluminium clofibrate	C10AB03
	gemfibrozil	C10AB04
	fenofibrate	C10AB05
	simfibrate	C10AB06
	ronifibrate	C10AB07
	ciprofibrate	C10AB08
	etofibrate	C10AB09
	clofibride	C10AB10
	choline fenofibrate	C10AB11
	clofibrate	C10AB01
	colestyramine	C10AC01
	colestipol	C10AC02
	colextran	C10AC03
	colesevelam	C10AC04
	niceritrol	C10AD01
	nicotinic acid	C10AD02
	nicofuranose	C10AD03
	aluminium nicotinate	C10AD04
	nicotinyl alcohol (pyridylcarbinol)	C10AD05
	acipimox	C10AD06
	nicotinic acid, combinations	C10AD52

### Tofacitinib A3921321 NON-INTERVENTIONAL STUDY PROTOCOL Final, Version 5.0, 11 February 2022

Class of drug	Drug	ATC code
	dextrothyroxine	C10AX01
	probucol	C10AX02
	tiadenol	C10AX03
	meglutol	C10AX05
	omega-3-triglycerides incl. other esters and acids	C10AX06
	magnesium pyridoxal 5-phosphate glutamate	C10AX07
	policosanol	C10AX08
	ezetimibe	C10AX09
	alipogene tiparvovec	C10AX10
	mipomersen	C10AX11
	lomitapide	C10AX12
	evolocumab	C10AX13
	alirocumab	C10AX14
	bempedoic acid	C10AX15
	inclisiran	C10AX16
	evinacumab	C10AX17
	volanesorsen	C10AX18

